## **17.0 MONITORING THE STUDY**

Clinical site monitoring is conducted to ensure that the rights and well-being of human subjects are protected, that the reported trial data are accurate, complete, and verifiable, and that the conduct of the trial is in compliance with the currently approved protocol/amendment(s), with GCP, and with applicable regulatory requirement(s). Each site will undergo periodic monitoring of the study, which involves a visit from a trained Sponsor representative. Monitoring visits may include, but will not be limited to, the following:

- Adherence of the protocol
- Verification of accuracy of study logs such as the Delegation of Responsibility, etc.
- Verification that informed consent is obtained for all subjects participating in the study in accordance with requirements described in the study protocol
- Verification of completeness of the Regulatory Binder.
- Source data verification with the eCRFs.
- Identification and action to resolve any issues or problems with the study.

Data are to be submitted as soon as possible after collection via e-CRF. Missing or unclear data will be corrected as necessary throughout the trial. Biosense Webster may request further documentation such as physician and/or cardiac EP lab procedure notes when complications or malfunctions are observed and reported.

Monitoring activities will be documented through such means as contact reports and follow-up summaries of status and action items. Further details on clinical monitoring are provided in the study specific monitoring plan.

## 17.1 Early Termination Monitoring Visit

If early termination of the study is required, each site will undergo a monitoring visit as described in the monitoring plan to conclude any outstanding issues, collect all outstanding CRF information, verify device accountability, and discuss any other items relevant to the conclusion of the study. Subjects will be notified of the termination of the study. Any enrolled subjects will continue to be followed per the study protocol requirements until a study closeout plan is implemented that outlines alternative follow-up procedures.

# **18.0 STATISTICAL ANALYSIS METHODS**

## 18.1 Study Design

Prospective, multicenter, non-randomized, clinical evaluation of the QDOT MICRO™ catheter compared to a historical control performance goal. There are two study arms for the treatment; Main Study, QDOT MICRO™ catheter with constant flow rate (8 mL/min) during QMODE+ RF application and second (variable flow) study, variable flow rate (4-15 ml/min) during QMODE+ RF application. QMODE RF applications will use the same flow rates for both studies.

The tral will enroll **185** evaluable subjects in the Main study and 92 subjects in the second (variable flow) study for a total of 277 subjects. The analysis for the Main study is a standalone analysis and it is not dependent on data from the variable flow study. The results from the variable flow study will only be used for additional claims.

## **18.2** Treatment Assignment

The treatment assigned for both studies is the QDOT MICROTM catheter. The difference in the 2 studies is the irrigation flow rate during QMODE+ RF application; Main study irrigation flow rate is 8 mL/min constant and the second study is variable flow of 4-15 mL/min (dependent on catheter tip temperature).

Enrollment into the two studies will be in a sequential fashion. The first 185 subjects will be enrolled in the Main study. Subjects enrolling after the completion of enrollment in the Main study will be enrolled into the second (variable flow) study.

## **18.3** Interval Windows

Refer to section 13.7 and Table 13.8A.

# 18.4 Primary and Secondary Endpoint(s), and Associated Hypotheses

The primary goal of the trial is to demonstrate safety and effectiveness. For each study to be successful, both safety and effectiveness endpoints must be statistically significant relative to their respective performance goals.

## Study Success

The study will be considered successful if the primary endpoints are met for main study. If the main study is not successful, the data for the second (variable flow) study will not

	Biosense Webster, Inc	
Version 5.0 – Feb 3, 2021	CONFIDENTIAL	Page 100 of 135

be submitted for labeling. The second (variable flow) study will be considered successful if both the primary safety and primary effectiveness performance goals are met.

# **18.4.1 Primary Endpoint(s) and Associated Hypotheses**

Acute Safety: The primary safety endpoint is the proportion of subjects with any Primary Adverse Event occurring within 7 days of ablation procedure. The PAE rate will be compared against an PG of 14%.

The primary safety endpoint will be assessed by testing the hypotheses:

 $H_0: p_s \ge 0.14$  vs.  $H_A: p_s < 0.14$ ,

where  $p_s$  is the proportion of patients with PAE at early onset (within 7 days of ablation procedure).

The primary safety analysis will be performed at the time of the interim analysis for the Main study. In the variable flow study, the primary endpoints will be evaluated after full 12-month follow-up is completed on all subjects.

**12-Month Chronic Effectiveness**: The primary effectiveness endpoint is the proportion of patients that are free from documented atrial arrhythmia (atrial fibrillation (AF), atrial tachycardia (AT), or atrial flutter (AFL)) episodes at Month 12 (that is, during the 9-month post-blanking period, i.e. Day 91-365).

The primary effectiveness endpoint will be assessed by testing the hypotheses:

 $H_0: p_E \le 0.50$  vs.  $H_A: p_E > 0.50$ ,

where  $p_E$  is the proportion of patients that are free from AF, AT, and AFL episodes at 12month follow-up (includes a 3-month blanking period).

In case early success is achieved, the study will continue to follow up the subjects for the full follow-up duration. The primary effectiveness endpoints based on full 12-month follow-up data will be descriptively summarized in subjects in the PP population. The primary effectiveness endpoint in the variable flow study will be evaluated at the end of the study, i.e. completion of 12-month follow-up in all subjects.

# 18.4.2 Secondary Endpoints and Associated Hypotheses

No formal statistical hypothesis and inferential statistics will be formulated and performed for the secondary safety and effectiveness endpoints.

Refer to Section 8.2.3.1 for secondary safety endpoint, and Section 8.2.3.2 for secondary effectiveness endpoints.

#### 18.4.3 Other Endpoints

No formal statistical hypothesis and inferential statistics will be formulated and performed for the additional safety and effectiveness endpoints.

Refer to Section 8.2.3.3 for additional endpoints.

#### 18.5 Levels of Significance

The type I error for the interim and final analyses of the primary endpoints for the main study is controlled at one-sided 2.5%. Two-sided 95% confidence intervals will be presented around the percentages unless otherwise specified. For the variable flow study, both primary endpoints will be tested at the end of the study at the 2.5% significance level, and all confidence intervals will be presented at the 95% confidence level unless otherwise specified.

#### 18.6 Analysis Set

The treatment for both studies is the QDOT Micro Catheter, there for the analyses sets are defined identically for both studies.

**Safety Population (SP) :** The Safety population will include all enrolled subjects who have the investigational device inserted, regardless if RF energy is delivered.

**Modified Intent-To-Treat (mITT) Population**: the modified Intent-To-Treat (mITT) population will consist of all enrolled subjects who have the investigational device inserted AND meet all eligibility criteria.

**Per Protocol (PP) Population:** The PP population will include subjects who satisfy the following criteria:

- o are enrolled and meet all eligibility criteria
- have undergone RF ablation
- $\circ\;$  are treated with the study catheters, and have been treated for the study-related arrhythmia

**CT/MRA (CTS) Population:** The CT/MRA set will consist of the first 40 subjects who are consecutively enrolled in the main study with 3-month CT/MRA assessment. The subject must have readable outcomes at baseline and 3 months.

## **18.7** Sample Size Justification

#### The Main study:

The Final analyses for primary safety and effectiveness endpoints will apply Bayesian methods and use a beta-binomial model after all subjects complete the 12 months

Biosense Webster, Inc

Version 5.0 – Feb 3, 2021 CONFIDENTIAL

follow-up (assuming early success is not achieved for the primary effectiveness endpoint). Non-informative Beta priors will be used for both safety and effectiveness endpoints. Trial simulations were performed to estimate the power for the success of the safety and effectiveness endpoints. Based on PG of 14% for the primary safety endpoint and PG of 50% for the primary effectiveness endpoint, the sample size of 185 subjects will provide above 80% power to declare success for both endpoints controlling the overall type-I error rate at one-sided 2.5% assuming the true PAE rate is 7% and the true effectiveness failure-free rate is 65%. It is also assumed that there are 5% and 12% dropout rates for the safety and effectiveness endpoints, respectively.

Simulations were also performed to estimate the overall type I error for this study under various hypothetical scenarios. The highest type I error rates were reached in the following two scenarios, including 1) the true primary safety rate was on the decision boundary (i.e. equal to 14%) and the device was assumed to be effective: type I error rate was 0.023, and 2) the true primary effectiveness rate was on the decision boundary (i.e. equal to 50%) and the devices was assumed to be safe: type I error rate was 0.011. As the primary safety or effectiveness moves away from the decision boundary, the overall Type-I error decreases. Therefore, considering all scenarios, the overall type I error for claiming success for both safety and effectiveness was controlled at 2.5%.

Based on the simulation results, the study is adequately powered to meet the primary safety and effectiveness endpoints and Type-I error for the overall trial success is controlled at 2.5%.

## The Second (variable flow) Study:

The analyses for primary safety and effectiveness endpoints in the variable flow study will apply Bayesian methods using a beta-binomial model with data borrowing from the Main study using a propensity score-integrated power prior approach. Based on a PG of 14% for the primary safety endpoint and a PG of 50% for the primary effectiveness endpoint, and allowing borrowing up to 91 subjects from QDOT MICRO (IDE # G180176) Main study, the sample size of 92 subjects in the variable flow study provides close to 80% power at a one-sided significance level of 2.5% to declare success for both the safety and effectiveness endpoints assuming the true PAE rate is 7% and the true effectiveness failure-free rate is 65%. Overall power for the variable flow study is maintained close to 80% when information from at least 80 subjects in the Main study is borrowed. It is also assumed that there are 5% and 12% attrition rates for the safety and effectiveness endpoints in the variable flow study, respectively.

## 18.8 Data Monitoring Committee

Data Monitoring Committee will be formed for this study and will evaluate data from both studies. An independent statistician will be responsible for conducting the interim analyses and reviewing the results with the designated Data Monitoring Committee

Biosense Webster, IncVersion 5.0 – Feb 3, 2021CONFIDENTIALPage 1

(DMC). The DMC charter will document the role and responsibilities of the committee, Sponsor and the independent statistician.

## **18.9** Analyses to be Conducted

#### **18.9.1** General Conventions

In general, descriptive statistics will be provided for all primary and secondary safety and effectiveness endpoints and other endpoints as appropriate. For continuous variables, number of subjects/events, mean, standard deviation, median, 25% percentile, 75% percentile, minimum, and maximum will be provided. For categorical variables, frequency and percentage will be presented for each category.

Confidence intervals for binary variables, including the primary outcome variables, will be computed using the exact binomial distribution. Categorical variables will be compared using Chi-square or Fisher's exact test. Continuous variables will be compared using ANOVA or Kruskal-Wallis test.

#### **18.9.2** Disposition of Study Subjects

Disposition and accountability of the study subjects will be summarized and listed.

## **18.9.3** Demographic and Baseline Characteristics

Demographic and baseline characteristics will be summarized and listed.

## **18.9.4** Analysis of Primary Endpoint Analyses

#### The Main study:

The final analyses for primary safety and effectiveness endpoints in the main study will apply Bayesian methods and use a Beta-Binomial model. A vague Beta(1,1) prior will be used for both safety and effectiveness endpoints.

If the primary safety endpoint is met (at the time of the interim analysis) and early success is achieved for the primary effectiveness endpoint, then the trial will be declared a success. If the safety endpoint is not met the study will be deemed unsuccessful. Under the success scenario, the study will continue to follow up the subjects for the full follow-up duration, and the primary effectiveness endpoint based on full 12-month follow-up data will then be descriptively summarized in subjects in the PP population. If early success is not achieved for the primary effectiveness endpoint, then the final effectiveness analysis for the main study will be based on complete follow-up data for effectiveness endpoint and will use a beta-binomial model.

Primary safety endpoint will be analyzed in the mITT population and primary effectiveness endpoint will be analyzed in the PP population.

Assuming early effectiveness success is not achieved, the trial will be considered a success if BOTH

Version 5.0 – Feb 3, 2021

Biosense Webster, Inc CONFIDENTIAL

$$\Pr(p_S < 0.14 | y, n) > 0.975$$

AND

 $\Pr(p_E > .50 | x, n) > 0.9775.$ 

These thresholds control the overall Type I error rate for the trial below one-sided 2.5% (see appendix C report for additional discussion of Type I error control).

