### 8.2.2 Primary Effectiveness Endpoint

The primary effectiveness endpoint is defined as the freedom from documented atrial fibrillation, atrial flutter and atrial tachycardia (AF/AFL/AT) (hereinafter collectively referred to as "atrial tachyarrhythmias") recurrence (episodes  $\geq$  30 secs on TTM or continuously recorded on the standard 12-leads ECG) during the evaluation period (Day 91-365) and freedom from the following failure modes:

- Acute procedural failure, including:
  - Failure to confirm entrance block in all pulmonary veins post-procedure,
  - Use of a non-study catheter to treat left atrial ablation targets and cavo-tricuspid isthmus
- Repeat ablation failure, including:
  - $\circ$  > 2 repeat ablation procedures with the study catheter during the 3-Month Blanking Period (Day 0-90) after the index ablation procedure.
  - Use of a non-study catheter to treat study arrhythmia ablation targets during the blanking period
  - Any repeat ablation procedure during the Evaluation Period.
- AAD failure: Taking a new AAD for AF or a previously failed AAD at a greater than the highest ineffective historical dose for AF during the evaluation period (refer to section 13.1 for details).

This study is designed to compare the primary effectiveness of the QDOT MICROTM Catheter to a pre-determined performance goal of 50%, which is indicated as the

	Biosense Webster, Inc	
Version 5.0 – Feb 3, 2021	CONFIDENTIAL	

minimum acceptable success rate at 12 months for a paroxysmal AF population in the 2017 HRS/EHRA/ECAS/APHRS/SOLAECE consensus statement.

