### 9.5 Subject Disposition

A subject is considered enrolled when they sign the informed consent. Because the treatment assignment is the same for both studies the subject disposition does not change for the second (variable flow) study.

- Enrolled Subjects: subjects who sign the informed consent.
- **Excluded Subjects**: subjects that are enrolled but never undergo insertion of the study catheter. Excluded subjects will not be included in the safety evaluation of the study catheter.
- **Discontinued Subjects**: subjects that have the study catheter inserted but are not treated with the study catheter (i.e., no RF energy applied). These discontinued subjects will be followed for 3 months and be part of the safety evaluation.
- **Evaluable Subjects**: enrolled subjects who meet the eligibility criteria and undergo ablation with the study catheter.
- Lost to Follow-up Subjects: subjects who are enrolled, but contact is lost after most recent follow-up visits (despite 3 documented attempts to contact the subject).
- Withdrawn / Early Termination Subjects: subjects who withdraw consent for study participation or are withdrawn by the investigator or are terminated from the study prior to completion of all follow-up visits.
- **Completed Subjects**: enrolled subjects who completed the 12-month followup visit and have not been excluded, discontinued, withdrawn, early terminated, expired or lost-to-follow-up from the study prior to the final study visit.

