## 18.9.8 Sensitivity Analyses

#### The Main study:

The primary safety endpoint will be analyzed in the Safety Population as sensitivity analyses. The primary effectiveness endpoint will be analyzed in the Safety Population for those subjects who have undergone RF delivery with the study catheter as sensitivity analyses. In addition, tipping point analysis[59] will be performed for the primary effectiveness endpoint in the PP population and for the primary safety endpoint in the mITT population to assess the impact of missing outcomes on study conclusions. These sensitivity analyses will be done after the 12 months follow-up is complete. Additional details will be defined in the SAP for the Main study.

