7.6 Analysis of Primary Effectiveness Endpoint

The primary effectiveness endpoint will be assessed by testing the following hypothesis:

$$H_0: p_E \le 0.50$$
 vs $H_A: p_E > 0.50$,

where p_E is the effectiveness success rate. The mITT Analysis Set is the primary analysis set for the primary effectiveness endpoint.

The primary analysis for the primary effectiveness endpoint will use complete follow-up data from the Variable Flow study with borrowing from the mITT analysis set in the Main study, and apply Bayesian testing using a beta-binomial model.

The primary effectiveness endpoint will be considered as success if

$$\Pr(p_E > 0.5 | x, n) > 0.975$$

where p_E is the 12-month effectiveness rate.

If the posterior probability of the effectiveness rate being greater than 50% is higher than 0.975, then the study will be considered to have demonstrated effectiveness of the device.

The Variable Flow study will be considered achieving study success when both the primary safety and primary effectiveness performance goals are met. The following additional

analyses will be performed at the time of the final effectiveness analysis. Similar to the safety sensitivity analyses, the posterior distribution for the effectiveness endpoint for each stratum is updated by incorporating the missing effectiveness outcomes according to each scenario. Borrowing from the main study remains unchanged from the primary analysis, i.e., sensitivity analyses will be performed for missing primary endpoint data in the Variable Flow study.

• Tipping Point Analysis

Tipping point analysis will be performed for the primary effectiveness endpoint in the mITT analysis set to assess the impact of missing outcomes in the Variable Flow study on the primary effectiveness analysis. The posterior distribution will be updated each time to evaluate whether a tipping point is identified.

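### In the protocol, Main primary effectiveness is analysed only in sets that require RF delivery, so eligible subjects with the catheter inserted but no RF drop out even when the catheter was the cause

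*Protocol*

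**What the plan says.** **Primary set.** Protocol 18.9.4, for the Main study: "Primary safety endpoint will be analyzed in the mITT population and primary effectiveness endpoint will be analyzed in the PP population". The interim rule in 18.9.6 names no set of its own, so 18.9.4 governs it.

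**Definitions (protocol 18.6).** PP subjects must be eligible, "have undergone RF ablation", and be treated with the study catheter. The mITT "population will consist of all enrolled subjects who have the investigational device inserted AND meet all eligibility criteria"; RF is not required.

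**The subjects in between.** Section 9.5 calls them Discontinued: "subjects that have the study catheter inserted but are not treated with the study catheter (i.e., no RF energy applied"). They are followed for 3 months and belong to the safety evaluation.

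**The endpoint.** Section 8.2.2 lists acute procedural failure among the failure modes, including "Failure to confirm entrance block in all pulmonary veins post-procedure".

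**Other Main effectiveness analyses.**
- 18.9.8, first sensitivity analysis: "The primary effectiveness endpoint will be analyzed in the Safety Population for those subjects who have undergone RF delivery with the study catheter".
- 18.9.8, effectiveness tipping point: PP.
- 18.9.5, secondary effectiveness: PP.
- 18.9.9, subgroups for primary effectiveness: PP.
- 18.4.1 and 18.9.4, the 12-month summary after early success: PP.
- 18.9.10, site homogeneity, and the 18.9.9 subgroups for acute effectiveness: no set named.

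**The sister study.** SAP 7.6 makes mITT the primary effectiveness set for Variable Flow, "with borrowing from the mITT analysis set in the Main study". SAP section 5 scores discontinuations related to the catheter as acute effectiveness failures, and says that unrelated ones are not.

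**The concern.** Whether a subject enters the Main effectiveness test depends on what happened after the catheter went in. A subject whose procedure stopped before RF because of the catheter cannot have had the veins isolated by it. On the wording of 8.2.2 this is an acute procedural failure, but the subject has left the analysis set before that definition can apply. The same subject, if eligible, stays in the Main safety test, which uses mITT.

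Removing such subjects can only raise the observed success rate. In a single-arm comparison with a fixed 50% goal, no control arm is subject to the same exclusion. At stake are the meaning of the Main success claim and, if the count is more than one or two, a result close to the pass boundary.

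**Working it through.** **1. The plan's own figures.** Inputs: N = 185 (18.7); goal 50%; Beta(1,1) prior; final threshold 0.9775 (18.9.4); interim threshold 0.9975 (18.9.6); dropout 12% for effectiveness and 5% for safety, per year (30.3.4). Appendix D Table 5 gives, at 65% failure-free and 7% PAE, power of 0.952 for effectiveness, 0.860 for safety and 0.817 for both.

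One-look exact check:
- Effectiveness: n = 185 × 0.88 ≈ 163. The smallest passing count is x = 95 and power is 0.969.
- Safety: n = 183 (5% per year over 90 days), pass if y ≤ 16, power 0.857.
- Both: 0.969 × 0.857 = 0.830.

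All three are within 2 points of the stated values. A simulation of the full design gives 0.79 for both at 12% yearly dropout and 0.82 at 9%. The stated power is not in dispute.

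**2. Effect of the exclusion, one look and complete data.** Suppose d of 185 mITT subjects had no RF and count as failures, and the true mITT success rate is 50%. The documents give no value for d, so d = 3 (1.6%) and d = 5 (2.7%) are assumptions. The PP success rate is then 0.5 × 185 / (185 − d). The rule is to pass if Pr(p_E > 0.5 | Beta(1 + x, 1 + n − x)) > 0.9775.

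| d | n | smallest passing x | PP success rate | Pr(pass) | x/185 |
|---|---|---|---|---|---|
| 0 | 185 | 107 | 0.500 | 0.0196 | 57.8% |
| 3 | 182 | 105 | 92.5/182 = 0.508 | 0.0374 | 56.8% |
| 5 | 180 | 104 | 92.5/180 = 0.514 | 0.0502 | 56.2% |

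**3. The same with the plan's interim and missing-data rule.** Section 18.9.7 keeps a failure even if the subject leaves later, and excludes failure-free subjects without 12 months of follow-up. That removes successes only, so it lowers the observed rate and works against the exclusion in step 2. The simulation used the three-piece hazard model and expected enrollment of Appendix D, both thresholds and this rule. Effectiveness-only false success, at a true mITT rate of 50%, is about:

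| yearly dropout | d = 0 | d = 3 | d = 5 |
|---|---|---|---|
| 12% | 0.6% | 0.9% | 1.5% |
| 9% | 1.0% | 1.5% | 2.1% |
| 7% | 1.1% | 1.8% | 2.7% |

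Simulation error is about 0.1 point. Table 5 prints 0.009-0.010 for effectiveness at 50%, which is closer to the 7-9% rows than to the 12% row. The 7% row lies below the plan's stated assumption.

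**4. At the pass boundary.** With 163 analysed, 95 successes give a posterior probability of 0.983. One added failure (95/164) gives 0.979, still a pass. Two (95/165) give 0.974, below 0.9775.

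**The case against.** **The offset within the analysis.** The 3.7% and 5.0% figures need complete data on every subject. Under the plan's 12% dropout the 18.9.7 rule pulls the other way, and false success stays below 2.5% for 3 or 5 exclusions. This stands. A reader might infer that the exclusion breaks the 2.5% limit; the documents do not support that. Only at 7% dropout with 5 excluded does the simulation slightly exceed it. The offset comes from an unrelated rule, however, and does not justify the exclusion.

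**The missing document.** A reader might infer that no Main effectiveness analysis anywhere counts these subjects. The supplied SAP covers Variable Flow only, and 18.9.8 defers detail to a Main SAP. The claim is limited to analyses in the protocol with a named set.

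**Who is a failure.** A reader might infer that every no-RF subject is a device failure. SAP section 5 says otherwise for discontinuations unrelated to the catheter. This stands too: the relevant count may be smaller than d. It does not remove the gap, because the protocol counts not even the catheter-related ones.

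**Denominator.** Section 18.1 speaks of 185 evaluable subjects, and 9.5 defines evaluable as having undergone ablation, so no-RF subjects could come on top of 185. Sections 8.1 and 18.2 instead speak of 185 enrolled. Step 2 takes 185 as the mITT count, which is an assumption.

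**Borrowing.** A reader might infer that the Main rate borrowed by Variable Flow differs from the Main rate tested. The named sets do differ, but SAP 7.4 borrows only subjects with non-missing endpoint data, and nothing says how Main no-RF subjects are scored. That they enter the borrowed rate is not established.

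**Scope.** RF-treated subjects without entrance block remain failures in PP. Only the pre-RF group is affected.

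**Conclusion.** The point holds as a gap in the protocol's Main effectiveness analyses. The primary set and all other named sets require RF delivery, so a catheter-related discontinuation before RF is not counted as a failure, whereas the sponsor's own plan for the sister study counts it. The direction favours the device.

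The size rests on the no-RF count, which the documents do not give. With none there is no effect, and with one a bare 95/163 pass survives. With 3 to 5, false success measured against the mITT rate rises by a factor of roughly 1.5 to 2.5, but under the plan's dropout assumption it stays within the 2.5% limit. The effect on the reported rate is modest. At the passing counts in step 2, PP gives 105/182 = 57.7% against 56.8% in mITT, and 104/180 = 57.8% against 56.2%. This is a low-cost improvement to make, not a demonstrated loss of error control.

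**What to change.** 1. Analyse Main primary effectiveness, interim and final, in mITT, with PP as supportive. At a minimum, replace the RF-conditioned sensitivity set in 18.9.8 with mITT.
2. Adopt the Variable Flow rule for Main: discontinuations related to the catheter are acute effectiveness failures. Add a version that counts all no-RF subjects as failures.
3. State in 18.9.7 that subjects scored as failures are not removed for incomplete follow-up. Changing the set alone is not enough, because Discontinued subjects have only 3 months of follow-up and could be excluded as failure-free with incomplete data.
4. Report the number of no-RF subjects and the reason for each.

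The cost is wording in the protocol and the Main SAP. Whether RF was delivered is known on the day of the procedure, so no extra follow-up is needed. The reported success rate may fall by up to about two points. If 3 or 5 of 163 analysed subjects were no-RF failures and the rest were 65% failure-free, one-look power for both endpoints would fall from 0.830 to 0.806 or 0.783.
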